8.1.4 Recording and Follow-up of Adverse Events

At every visit during the study period, the subject will be asked a nonleading question such as "Have you had any health problems since you were last asked/seen?" All AEs reported in response to questioning, as well as AEs reported spontaneously and occurring at any other time, will be recorded on the "Adverse Event" page(s) of the eCRF, regardless of causality.

If an AE fulfils any of the criteria for a SAE, both the AE pages of the eCRF and the SAE Form must be completed.

All abnormal laboratory results that are clinically significant and, abnormalities in physical examinations and vital signs are to be recorded as AEs. Results of 12-lead ECG will be immediately analysed by a cardiologist or qualified investigator, and any clinically relevant findings are also to be recorded as AEs. ECG results will also be reviewed centrally. If an abnormal laboratory (e.g. electrolytes disorders), physical examination, ECG, or vital sign finding meets any of the criteria for an SAE, it must be reported on an SAE Form.

The investigator should report a diagnosis or a syndrome rather than individual signs or symptoms. The investigator should also try to separate a primary AE considered as the foremost untoward medical occurrence from secondary AEs which occurred as complications

For both serious and nonserious AEs, documentation must be supported by an entry in the subject's hospital notes. The following information should be captured for all AEs: date of onset

and resolution, severity of the event, assessment whether the event was serious or nonserious, investigator's opinion of the relationship to investigational drug, treatment required for the AE, action taken with IRPP or OPS301 if applicable, and information regarding resolution/outcome.

8.1.4.1 Reporting of Adverse Events

Any AE/SAE occurring during the study, from informed consent up to 6 months after last study drug administration, must be reported to the sponsor.

Up to 6 months after the last study drug administration, all AEs/SAEs will be collected unless NET therapies are started, then only AEs/SAEs considered by the investigator to be related to the study drug/procedure will be collected. From 6 months after the last study drug administration until 2 years after the EOCT/EOAC/EW Visit, withdrawal of consent, lost to follow-up or death, all AEs/SAEs related to the study drug/procedure will be collected.

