3.1.4 Long-Term Follow-Up

The long-term follow-up period will start after the EOCT/end of additional cycles (EOAC)/early withdrawal (EW) Visit.

Tumour assessments will be performed every 3 months (± 2 weeks) until whichever occurs first: documented disease progression (radiological or clinical as per the investigator's judgment), 2 years after the EOCT/EOAC/EW Visit, withdrawal of consent, lost to follow-up or death.

Safety assessments, and the subject's status, will be performed every 3 months (± 2 weeks) until whichever occurs first: 2 years after the EOCT/EOAC/EW Visit, withdrawal of consent, lost to follow-up or death; please refer to Section 8.1.4.1.

After the long-term follow-up period is completed i.e. 2 years after the EOCT/EOAC/EW Visit, all subjects will be invited to participate in a safety surveillance study, as part of a separate study protocol. All subjects will be asked to sign a new informed consent form to enter this study. The purpose of the safety surveillance study is to monitor any long-term effects of ^{177}Lu -OPS201 up to 5 years from the first dose of ^{177}Lu -OPS201.

The schedule of assessments is provided in a flow chart (see Section 5.1) and is listed in Section 5.2. Unless otherwise specified, all assessments will be performed by the investigator or accredited study personnel.

Extra visits, examinations, tests and interventions can be performed at any time if clinically indicated, as judged by the investigator.

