s central read of ceCT/MRI is performed during Core Trial and additional optional cycles; local read is performed during the 2-year LTFU period. ⁶⁸Ga-PET scan may be performed during the treatment period (Core Trial and Additional Cycles) and the 2-year LTFU period, if deemed necessary by the investigator.

t sstr scan should be performed (unless already performed within 6 months prior to Day 1) Local SRS eligibility read is performed at screening.

u postdosing imaging at 4 hours ±10 min. In case of misadministration (such as spillage or interruption of the infusion), an additional whole body scan is required shortly after the end of infusion and before the first bladder emptying (see Section 9.2.1 Whole Body Scan).

v CCI

w up to 6 months after the last study drug administration, all AEs/SAEs will be collected unless new NET therapies are started, then only AEs/SAEs related to the study drug/procedure will be collected. From 6 months after the last study drug administration until 2 years after the EOCT/EOAC/EW Visit, withdrawal of consent, lost to follow-up or death, all AEs/SAEs related to the study drug/procedure will be collected.

The total volume of blood drawn for all evaluations throughout this study is up to 306.0 mL in Part A and up to 563.5 mL in Part B across 23 visits (Part A) or 41 visits (Part B) and will not exceed 77.5 mL at any one visit and 158.5 mL within 1 month (see Section 5.3 and Table 9). The total amount will be greater for subjects participating in Part B, which includes OPS201 PK, blood for CCI in all sites (5 mL of whole blood for serum) and CCI

The total volume of blood for biobanking is 33 mL, which is an optional assessment.

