5.2.9 Long-term Follow-up Visits (1 to 8)

Long term follow-up visits will be carried out every 3 months for 2 years starting 12 weeks after the EOCT/EOAC/EW Visit (see Section 3.1.4). In the long-term follow-up phase, deviations (± 2 weeks) from the time schedule are not recorded as significant deviations.

Tumour assessments will be assessed every 3 months (± 2 weeks) until whichever occurs first: documented disease progression (radiological or clinical as per the investigator's judgment), 2 years after the EOCT/EOAC/EW Visit, withdrawal of consent, lost to follow-up or death.

Safety assessments, and the subject's status, will be performed every 3 months (± 2 weeks) until whichever occurs first: 2 years after the EOCT/EOAC/EW Visit, withdrawal of consent, lost to follow-up or death.

After the long-term follow-up period is completed i.e. 2 years after the EOCT/EOAC/EW Visit, all subjects will be invited to participate in a safety surveillance study, as part of a separate study protocol. All subjects will be asked to sign a new informed consent form to enter this study. The purpose of the safety surveillance study is to monitor any long-term effects of ^{177}Lu -OPS201 up to 5 years from the first dose of ^{177}Lu -OPS201.

Efficacy assessments

- CT/MRI (same method as in Screening Visit); ± 2 weeks' window allowable
- survival
- tumour markers.

Long-term safety assessment

- vital signs and 12-lead ECG
- physical examination
- laboratory tests (biochemistry, haematology, and urinalysis)
- AEs/concomitant medications (NET only) (see Section 8.1.4.1).

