8.1.5 Reporting of Serious Adverse Events

An SAE is classified as any untoward medical occurrence that at any dose:

- Results in death, or;
- Is life threatening, that is any event that places the subject at immediate risk of death from the event as it occurred. It does not include an event that, had it occurred in a more severe form, might have caused death, or;
- Requires inpatient hospitalisation or prolongation of existing hospitalisation, excluding admission for social or administrative reasons (see further), or;
- Results in persistent or significant disability / incapacity, where disability is a substantial disruption of a person's ability to conduct normal life functions, or;
- Is a congenital anomaly / birth defect in the offspring of a subject who received the IRPP or OPS301 if applicable.
- Is an important medical event that may not result in death, be life threatening, or require hospitalisation when, based upon appropriate medical judgement, may jeopardise the subject and may require medical or surgical intervention to prevent one of the outcomes listed in this definition. Examples of such medical events include allergic bronchospasm requiring intensive treatment in an emergency room or at home, blood dyscrasias or convulsions that do not result in in-patient hospitalisation, or the development of drug dependency or drug abuse.

In addition to the above criteria, any additional AE that the sponsor or an investigator considers serious should be immediately reported to the sponsor and included in the safety database. This includes any suspected or confirmed coronavirus COVID-19 (SARS-CoV-2) infection (seriousness criteria should be "other medically significant" if no other seriousness criteria are present (e.g. hospitalisation)).

- Hospitalisation is defined as any inpatient admission (even if less than 24 hours). For chronic or long-term inpatients, inpatient admission also includes transfer within the hospital to an acute/intensive care inpatient unit. (NB: only the inpatient admission not related to IRRP admission and in link with reportable SAE per protocol definition will be recorded in eCRF).

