- Prolongation of hospitalisation is defined as any extension of an inpatient hospitalisation beyond the stay anticipated/required in relation to the original reason for the initial admission, as determined by the investigator or treating physician. For protocol-specified hospitalisation in clinical studies, prolongation is defined as any extension beyond the length of stay described in the protocol. Prolongation in the absence of a precipitating, treatment emergent, clinical AE (i.e. not associated with the development of a new AE

or worsening of a pre-existing condition) may meet criteria for "seriousness" but is not an adverse experience and thus is not subject to immediate reporting.

- Preplanned or elective treatments/surgical procedures should be noted in the subject's screening documentation. Hospitalisation for a preplanned or elective treatment/surgical procedure should not be reported as an SAE unless there are complications or sequelae which meet the criteria for seriousness described above.

Planned hospitalisations that occur exclusively for study procedures must not be documented as SAEs.

Actions and reporting obligations in case of SAEs

All SAEs (as defined above), regardless of treatment group or of suspected relationship to IRPP or OPS301 if applicable, must be reported immediately. Therefore, all pertinent questions in the eCRF's Safety Report Section must be answered and the form signed. This triggers immediate notification of the sponsor through an email alert. The SAEs should be reported to the sponsor within 24 hours of awareness by completing an Ipsen SAE paper form included in the site folder and sending it to the sponsor by e-mail (preferably) or fax.

For SAE reporting:

Email: PPD

Fax:

The following information is the minimum that must be provided to the sponsor pharmacovigilance contact within 24 hours for each SAE:

- study number
- site number
- subject number
- AE
- IRPP (¹⁷⁷Lu-OPS201) information with administration date/dose/radioactivity
- OPS301 information with administration date (if applicable)
- investigator's name and contact details.

If the fall back solution was used for reporting an SAE, an Ipsen SAE form must be filled with all available details (as many as possible) within 24 hours and sent to Ipsen within 24 hours. The event data must still be entered by the site into the eCRF as soon as technical problems have been solved to ensure that all events are consistently entered into the study database.

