- t sstr scan should be performed (unless already performed within 6 months prior to Day 1) Local SRS eligibility read is performed at screening.
- u postdosing imaging at 4 hours ±10 min. In case of misadministration (such as spillage or interruption of the infusion), an additional whole body scan is required shortly after the end of infusion and before the first bladder emptying (see Section 9.2.1 Whole Body Scan).
- v at additional optional Visit 4 and Visit 5, no samples for pituitary markers, biobanking and exploratory biomarkers will be collected, except those for tumour markers. At the EOAC/EW Visit during additional cycles, no samples for biobanking and exploratory biomarkers will be collected, except those for tumour markers, and pituitary markers.
- w up to 6 months after the last study drug administration, all AEs/SAEs will be collected unless new NET therapies are started, then only AEs/SAEs related to the study drug/procedure will be collected. From 6 months after the last study drug administration until 2 years after the EOCT/EOAC/EW Visit, withdrawal of consent, lost to follow-up or death, all AEs/SAEs related to the study drug/procedure will be collected.

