3.2.1.2 Adverse events

All AEs will be recorded and graded by investigators using the NCI CTCAE classification v5.0 and will be coded using the Medical Dictionary for Regulatory Activities (MedDRA) Version 21.1 or higher and will be classified by MedDRA preferred term and system organ class.

Listings will be presented and sorted by study part, cohort (part B only), radioactivity level adapted or not (part B only), subject number, start time of AEs, primary system organ class, preferred term and verbatim text for all adverse events recorded during the study.

Listings of all adverse events, serious adverse events (SAE), adverse events leading to withdrawal, adverse events leading to dose reduction, adverse events leading to dose interruption, adverse events leading to dose delayed, adverse events with CTCAE Grade 3,4 and 5 and listings of deaths will also be presented.

Treatment Emergent Adverse Events (TEAE) will be flagged (*) in the adverse events listing and will be summarised.

A TEAE is defined as any adverse event that occurs up to 6 months (180 days) post last dose if:

- (1) it was not present prior to receiving the first dose of IRPP (or OPS301 if applicable), taking into account the time of administration and the time of AE, or
- (2) it was present prior to receiving the first dose of IRPP (or OPS301 if applicable) but the intensity/grade increased during the active phase of the study, taking into account the time of administration and the time of AE, or
- (3) it was present prior to receiving the first dose of IRPP (or OPS301 if applicable), the intensity/grade is the same but the causality changed to “related” during the active phase of the study, taking into account the time of administration and the time of AE.

Phase of the study will be defined into 3 time periods:

- period 1: treatment intake up to 56 days/8 weeks (corresponding to 8 half-lives of the ¹⁷⁷Lutetium rounded to the upper number of weeks, 162 hours * 8 + 2 days) after last dose
- period 2: 57 days up to 6 months post last dose
- period 3: after 6 months of last dose until 2-year follow-up period /death or lost to follow-up

An overall summary table (by period 1, 2 and 1+2) of all treatment emergent adverse events will be presented by study part, cohort (part B only) and overall using the Safety Analysis Set. This table will be also repeated for period 3.

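### From 6 months after the last dose only related AEs/SAEs are collected, with no exception for late myelodysplastic syndrome or acute leukaemia, while section 8.1.5 asks for all SAEs without an end date

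*Protocol*

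**What the plan says.** Protocol section 8.1.4.1 sets the collection window. All AEs and SAEs are collected up to 6 months after the last administration. If a NET therapy starts before then, only events the investigator considers related are collected. For the remaining time, up to the close of the 2-year long-term follow-up, the rule is narrower. It names the stopping points and then what is collected: "lost to follow-up or death, all AEs/SAEs related to the study drug/procedure will be collected".

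The same rule stands in the schedule (Protocol Table 7 footnote r and Table 8 footnote w): "unless new NET therapies are started, then only AEs/SAEs related to the study drug/procedure will be collected". It is copied into SAP Table 2 footnote r and Table 3 footnote w, with the later window worded as "From 6 months after the last study drug administration until 2 years after the EOCT/EOAC/EW Visit, withdrawal of consent" and so on. Long-term follow-up is sent to this rule twice. Section 3.1.4 ends its list of stopping points with "lost to follow-up or death; please refer to Section 8.1.4.1", and section 5.2.9 lists "AEs/concomitant medications (NET only) (see Section 8.1.4.1").

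Section 8.1.5 reads differently: "All SAEs (as defined above), regardless of treatment group or of suspected relationship to IRPP or OPS301 if applicable, must be reported immediately". It states no end date. Its examples of important medical events include "blood dyscrasias or convulsions that do not result in in-patient hospitalisation". Section 8.1.4 also records AEs at every visit in the study period whatever their cause.

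SAP section 3.2.1.2 reports late events under "period 3: after 6 months of last dose until 2-year follow-up period /death or lost to follow-up", with a summary table and a listing.

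**The concern.** Safety and tolerability is the primary objective. Protocol section 1.3.6.2.2 itself names myelodysplastic syndrome and acute myelogenous leukaemia as sporadic events reported after this class of therapy. Such diagnoses can arise late, when the related-only rule applies. Whether one is entered then depends on an open-label causality judgement and on which section the site follows.

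The weak spot is a subject who has moved to another NET therapy. Section 6.3.6 foresees later chemotherapy or radionuclide therapy. Starting one supplies an alternative cause, which section 8.1.2.2 accepts as a ground for calling an event not related, and it also ends the collection of unrelated events. A period 3 table showing no cases could then mean no cases judged related.

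**Working it through.** The plan states no figure to reproduce here. The check is mainly a reading of the text, with some arithmetic for scale.

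**1. Which events must be entered?** Take an acute leukaemia diagnosed 14 months after the last dose and judged unrelated.
- Under 8.1.4.1 and the schedule footnotes it is not collected.
- Under 8.1.5, read literally, it is reported at once.
- The AESI route does not help. Protocol section 8.1.3 covers allergic or immunological events, and SAP sections 3.2.1.2 and 5 limit AESIs to related events on the day of dosing.
- No exception by diagnosis appears in the protocol body or the SAP. The protocol appendices, the eCRF guideline and the surveillance protocol are not in the text reviewed.

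**2. How much calendar time falls under the related-only rule?**
- Last dose to EOCT/EOAC/EW: 8 weeks = 56 days.
- Long-term follow-up: 2 years = 730 days.
- Full collection: 6 months = 180 days (SAP 3.2.1.2).
- Total after the last dose: 56 + 730 = 786 days.
- Related-only: 786 − 180 = 606 days; 606/786 = 77%. An early NET therapy lengthens it.

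**3. What would one case do to the reported frequency?** Planned numbers run from 6 + 25 = 31 to 55 subjects. Exact (Clopper-Pearson) 95% intervals:

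| Cases | N = 31 | N = 55 |
|---|---|---|
| 0 | 0% (0 to 11.2%) | 0% (0 to 6.5%) |
| 1 | 3.2% (0.08 to 16.7%) | 1.8% (0.05 to 9.7%) |

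The intervals for 0 and 1 case overlap almost entirely. What changes is whether the event is reported at all.

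**4. How many cases might be missed?** The documents give no event rate. For scale only, with every input assumed except N:

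missed = N × 2-year risk × share arising after the cut-off × share judged unrelated and not entered

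- Low: 31 × 0.01 × 0.5 × 0.05 = 0.008.
- High: 55 × 0.04 × 1.0 × 0.20 = 0.44.
- High, but half arising late: 55 × 0.04 × 0.5 × 0.20 = 0.22.

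This is an illustration, not an estimate.

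**The case against.** The case for leaving the text alone is substantial.

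- **Attribution leans towards related.** Section 8.1.2.2 requires good reasons and sufficient information to rule out a causal link, and the sponsor reviews the call. For a diagnosis the protocol already associates with the drug class, related is the natural default.
- **Sequelae are followed.** Section 8.1.1 follows an AE and its sequelae beyond the last visit, so a myelodysplastic syndrome growing out of a recorded cytopenia would be pursued.
- **The blood counts stay visible.** Haematology is taken at every long-term visit. SAP section 3.2.1.3 grades it, lists Grade 3 and 4 and prolonged toxicities, and gives shift tables, with no filter on causality. Section 8.1.2.4 lets an abnormality become an AE on sponsor review.
- **Source records exist.** Section 13.3 requires SAEs in the subject's notes and full source data verification.
- **There is later surveillance.** Sections 3.1.4 and 5.2.9 invite all subjects to a study of long-term effects up to 5 years from first dose.
- **The sections can be reconciled.** 8.1.5 can be read as the procedure for SAEs inside the 8.1.4.1 window. A site reading it literally over-reports, which is the safe direction.

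Most of this stands and makes a missed case unlikely, but none of it requires the diagnosis to be entered in this trial. Sponsor review acts on events already recorded. Laboratory listings show a cytopenia, not a diagnosis. Verification against source does not call for an event the window excludes. The surveillance study needs a separate protocol and new consent, and starts only after the 2-year follow-up. The reconciled reading of 8.1.5 is reasonable, but it confirms that the unrelated late case is not collected.

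Three stronger readings are tempting. A reader might infer from the 77% that late marrow toxicity goes unobserved for most of follow-up; the continuing haematology contradicts that. A reader might take the mention of myelodysplastic syndrome in section 6.5 as a second naming of a late class risk; that section concerns managing an accidental overdose. A reader might extend the stated risk to all second malignancies; the protocol names only the two marrow diagnoses.

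**Conclusion.** The point holds as a small gap in ascertainment and an unclear boundary between two sections. A myelodysplastic syndrome or acute leukaemia arising more than 6 months after the last dose, or after a new NET therapy, and judged unrelated need not be entered as an AE or SAE. The period 3 outputs could then lack the diagnosis.

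The number of missed cases cannot be estimated from the documents and is probably well below one; the range of about 0.01 to 0.44 rests on assumed inputs. The 606 days are time under the rule, not lost information.

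A reader might infer that the safety results are biased or that dose selection is affected. The documents do not support that. DLTs must be related to the product, so an event judged unrelated cannot be one. The review board's decisions are tied to Cycles 1 to 3 (SAP section 3.2.19), and TEAEs end at 180 days. The case for change is that entry of a named late harm, in a trial whose primary objective is safety, should not turn on an open-label attribution. It is a cheap improvement of low priority.

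**What to change.** At the next amendment, add one sentence to Protocol section 8.1.4.1, to Table 7 footnote r and Table 8 footnote w, and to the SAP copies: myelodysplastic syndrome and acute leukaemia, and preferably any new primary malignancy, are recorded as an AE/SAE regardless of causality or new NET therapy until the end of the 2-year long-term follow-up, with causality recorded as an attribute. Extending it to any new primary malignancy is a preference, not something the protocol's stated risks require.

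Cross-refer 8.1.5 to 8.1.4.1 only together with this exception. On its own, the cross-reference would narrow SAE reporting.

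The existing 3-monthly visits suffice. The cost is a few more AE records and updated eCRF and site instructions at about 20 centres. Ethics review is likely to be needed for a change in safety collection (section 13.1.1), and section 14.1 discourages amendments once the study runs. That is why it should travel with another amendment and not prompt one.
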